9.1 Study population and trial setting

Our *study population* will be adult (≥ 18 years) PLHIV admitted to hospital and living in the catchment areas of 4 district hospitals in Mozambique and Tanzania.

This project is part of the EDCTP2 programme supported by the European Union

These two countries are included in the World Health Organization's high TB and HIV burden country list. In 2020 Mozambique and Tanzania had estimated TB incidence rates of 368 and 222 per 100 000 population respectively. The prevalence of HIV among new TB patients was 27 and 21% in 2020, respectively. The following table shows basic epidemiological indicators from the World Tuberculosis Report 2021 released by the World Health Organization.

| | Mozambique | Tanzania |
|---|------------|----------|
| TB incidence Rate (per 100 000 population) | 368 | 222 |
| HIV-positive TB incidence (per 100 000 population) | 101 | 47 |
| HIV-positive TB mortality (per 100 000 population) | 20 | 16 |
| Proportion of pulmonary TB who are bac confirmed (%) | 35% | 44% |
| TB treatment coverage (%) | 84% | 64% |
| TB case fatality ratio (%) | 11% | 22% |
| TB patients with known HIV status who are HIV-positive (%) | 27% | 21% |
| TB treatment success in HIV positive patients (2019)(%) | 88% | 90% |

Table 1. Basic World Health Organization TB burden of disease indicators (year 2020)⁴²

Four research institutions from 2 different countries will be recruiting participants for the trial at associated district hospitals (non-referral hospitals). All the research sites have:

- Capacity to enroll at least 270 eligible patients in a year.
- Continuous power supply
- Access to laboratory testing which can provide Ultra results and other relevant TB tests (AlereLAM) within 24 hours.
- Access to CD4 cells count testing and blood chemistry services.
- Adequate space for the research team to work in or to erect a temporary structure if the existing facility is not adequate to accommodate the research team.
- At least one physician on the research team with experience in management of patients with TB and HIV in order to make the relevant clinical decisions.
- Storage capacity for samples that will be analyzed at a later stage.

This project is part of the EDCTP2 programme supported by the European Union

9.1.1 Mozambique

9.1.1.1 Manhiça District Hospital (MDH) and Xinavane Rural Hospital (XRH) are two health facilities located in the district of Manhica, 80 and 120 km north from Maputo (respectively). MDH is a 110-bed rural hospital (60 beds in the adult ward), receiving referrals from 11 health care centers of the district. It is adjacent to Centro de Investigação em Saúde de Manhiça (CISM), which provides support with clinical staff and performing some of the laboratory procedures for the hospital. It offers obstetric services including obstetric emergency care, operation room and, in collaboration with CISM, a morbidity surveillance 24h 7 days per week, hospital-based morbidity surveillance system for children under 15 years of age attending the MDH. XRH is a 50-bed rural hospital, 50km from MDH with 40 beds in the adult ward, receiving referrals from 3 health care centers of the northern part of Manhiça district. Both hospitals have access to smear microscopy, GeneXpert, X-Ray facilities.

XRH is a 50-bed rural hospital (40 beds in the adult ward), receiving referrals from 3 health care centers of the northern part of Manhiça district. XPH is a provincial 40 – bed provincial hospital in the adult ward and MHC a relatively small health centre with a hospitalization capacity of 10 beds in the adult ward.

Additional sites such as the Maracuene, Magude and Macia Health Centres could be considered during the study if the recruitment rate in the MDH and XRH is inadequate. These 3 Health Centres are relatively small health centres surrounding the Manhiça District Hospital, located at 50, 150 and 160 km from Maputo (respectively), with a hospitalization capacity of 10, 54 and 31 beds (respectively) in the adult wards.

9.1.1.2 Mavalane General Hospital (MGH) and José Macamo General Hospital (JMGH) are hospitals located in Maputo city, with 72 and 70 adult beds respectively. Both hospitals collaborate with the Instituto Nacional de Saúde (INS), the national state funded health research institution in Mozambique. Both hospitals have access to smear microscopy, GeneXpert®, X-ray and CD4 cell count and HIV testing. Both hospitals serve some of the poorest regions of the city, have integrated Emergency Department (for children and adults), with those requiring intensive care transferred to Maputo Central Hospital.

9.1.2 Tanzania

9.1.2.1 NIMR Mbeya Medical Research Center is located on the same ground of the Mbeya Zonal Referral Hospital (MZRH), a public tertiary healthcare facility serving a population of about 8 million people in Southwestern regions of Tanzania. MZRH has the average number of hospital admissions

This project is part of the EDCTP2 programme supported by the European Union

of 30,000 per year and total of 400 bed capacity. MZRH admit over 200 HIV positive patients per month. NIMR work very closely with MZRH which provide a pool for recruitment of participants into various research studies carried out by NIMR. For this study recruitment of study participants will be conducted within the inpatient ward of MZRH and Mbeya Regional Referral hospital (MRRH). MRRH is a 150-bed regional hospital located in Mbeya city, Tanzania. It receives around 100 to 150 admissions of HIV infected patients per month. It works closely with NIMR Mbeya Center. It has microscopy, GeneXpert and X-ray facilities. Sputum, urine and other samples will be processed and tested at the NIMR laboratory.

9.1.2.2 St Francis referral hospital (SFRH) is located in the south-east of Morogoro region in Kilombero district. SFRH is a non-profit making organization belonging to the Roman Catholic Dioceses of Ifakara. It is a 371 beds Hospital and was declared a District (Council) Designated Hospital for Kilombero and Ulanga Districts in 1976 with catchment population of about 600,000 habitants and in 2010, the hospital was upgraded to the level of Referral Hospital. SFRH offers preventive, curative, rehabilitative and teaching services. SFRH is divided into departments for Surgery, Internal Medicine, Gynecology and Obstetrics, Pediatrics, Chronic Diseases and Intensive Care. Additionally, there are outpatients' departments and wards for Tuberculosis, Dental Medicine, Physiotherapy, Occupational Therapy, Psychiatry, Leprosy, Rehabilitation, an X-ray department, laboratory and a special laboratory for the production of infusions. SFRH in collaboration with the Ifakara Health Institute runs a HIV cohort with over 11,000 HIV positive patients ever enrolled. The cohort has been running since 2005. The average number of inpatients treated per year is 16,480.

9.2 Participant eligibility criteria

9.2.1 Pre-eligibility screening criteria

Adult HIV-positive patients admitted in the hospitalization wards of the participating hospitals.

9.2.2 Inclusion Criteria:

1. Adults (18 years old and above)
2. Confirmed HIV infection (including both antiretroviral (ART)- naïve and experienced)
3. Admitted to the hospital (adult medical wards) at the time of enrolment.

9.2.3 Exclusion criteria:

1. Unable to provide informed consent (if no authorized relatives are in the position to

This project is part of the EDCTP2 programme supported by the European Union

provide the consent)

2. Living outside the catchment area of the participating hospital(s)
3. With plans to migrate outside the catchment area within 2 months after recruitment.
4. Currently receiving anti-TB therapy or having received anti-TB therapy (or a TB diagnosis) in the last 6 months prior to enrolment
5. Currently receiving or having received preventive TB treatment in the preceding 6 months
6. Patients admitted for traumatic reasons, acute abdomen, delivery or pregnancy (maternal conditions), or for planned/scheduled surgery.
7. Referred from other reference hospital.
8. Positive result to a SARS-CoV-2 test (RT-PCR, antigen test, or other similar test that might define COVID-19 case in the study site)*

*AND patients under investigation for COVID-19 if this situation hinders the execution of study activities (as judged by the site PI)

9.3 Sample size

In order to detect a 36.8% relative difference (26% vs. 19%) in the proportion of admitted PLHIV who are bacteriologically confirmed TB positive between the intervention and control arm, the study will require a total of 586 participants to be enrolled per trial arm, whereby drop-out rates are considered (details see below). For both arms together, this yields 1172 patients in total. Given that 4 sites will be recruiting patients, this represents a mean of 293 participants per site (147 per arm at each site). Further details on sample size estimation can be found in (statistical considerations).

10. Study procedures

10.1 Pre-eligibility screening

Initial pre-eligibility based on HIV status will be assessed by study staff, who will visit the adult medical wards every morning to identify any newly admitted patients. HIV documentation can be written proof of a positive HIV test, CD4 count records or ART prescription. From the information available in patient registers and/or patient files, only those with unknown or documented HIV-positive status will be approached to participate in the study. Routine health personnel need to be aware of the study and contact study personnel whenever a new admission occurs.

For those with unknown HIV status, a rapid antibody-based test will be performed (further details under laboratory procedures) by authorized personnel (after ICF is obtained).

This project is part of the EDCTP2 programme supported by the European Union

Basic anonymized information on participants who are admitted in the adult ward but not enrolled in the study will be recorded in a pre-screening log which should include: age, gender and the reason not eligible for trial participation, or if they are eligible but declined.

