As part of a secondary objective, we will retrospectively collect data of a cohort of consecutively hospitalized HIV-positive patients that were admitted prior to the trial initiation (**third arm**), that will be used to compare the difference between the intervention arm or control arm with the real standard of care practiced at the sites.

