10.18 Retrospective data collection

Given that our control arm may not represent the local standard of care across sites, we will compare the main study endpoints of both study arms with a third cohort of patients, which follows the real standard of care at the different sites. We will retrospectively collect data of a cohort of consecutively hospitalized HIV-positive patients that were admitted prior to the trial initiation. Data to allow the evaluation of primary objectives will be collected from medical records (source documents) in an anonymized fashion. We aim to collect data from patients who were admitted to the site two months or more before the day of the trial first study patient recruitment. Patient records will be selected from consecutive admissions from that day backwards until completing the sample size (around 147 cases per site). Data collection will be obtained retrospectively in order to capture the real practice at the different sites, including potential phone calls to confirm the life status of the patients after two months of hospitalization, minimizing the effect of a potential Hawthorne effect. Given the complexity and often impossibility of obtaining informed consent from patients that have been discharged, no informed consent will be sought for these patients. This IC exemption is an exception contemplated in the International Ethical Guidelines for Health-related Research Involving Humans of the Council for International Organizations of Medical Sciences (CIOMS) (Geneva, 2016). The study has not been powered to detect differences in the primary endpoint between intervention or control arm and the retrospective cohort (which may vary between sites). This is a secondary objective that will be analyzed at site level.

11. Schedule of visits (table 2)

| | Day 0 (recruitment) Control arm | Day 0 (recruitment) Intervention arm | Day 0-3 (<72h) | Daily | At discharge If discharged before day 28/56 | Week 4 | Week 8 +/- 3 days |
|--|--|---|-------------------|-------|---|--------|-----------------------------|
| Baseline Evaluation | | | | | | | |
| Informed consent | X | X | | | | | |
| Eligibility criteria verified | X | X | | | | | |
| CD4 count / Viral Load ^{&} | X | X | | | | | |
| Locator information | X | X | | | | | |
| Brief medical history | X | X | | | | | |
| Proof of HIV status stored | X | X | | | | | |
| WHO Symptom screening | X | X | | | X | | |

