12.4 HIV testing: Rapid point-of-care antibody-based HIV testing will be performed in those patientswith unknown or undocumented HIV status using fingerprick blood. Testing will be done by trained health care workers. If the result of the first "rapid" test (Determine®, Abbott Laboratories, USA) is positive, a second confirmatory test will be performed. CD4 counts will be obtained fromTB cases coinfected with HIV (if no recent documented CD4 counts are available-within last 3 months)

This project is part of the EDCTP2 programme supported by the European Union

as well as all newly identified HIV-positive cases. CD4 testing will be done at each site using point of care PIMA equipment or FACSCalibur flow cytometers. Newly diagnosed HIV- positive patients will be referred to appropriate counselling services at each of the sites.

12.5 Sample Storage details:

Storage of all specimens will follow detailed SOP which will be similar at all participating sites.

Specimen storage is not a mandatory component of the protocol, but will be encouraged to accomplish exploratory objectives and retrospective testing. Storage should be done the same day of sample collection.

12.5.1 Urine samples. After removing necessary volumes for Ultra and AlereLAM testing, transfer raw urine (12 ml) to a sterile 50ml tube. Aliquot the supernatant in two 3.5 ml aliquots. Aliquots should be stored at -80 or -70°C. In case no criteria for AlereLAM testing is in place in the control arm, urine would still be collected for storage.

12.5.3 Tongue swabs samples: Two tongue swabs will be collected. After sample collection, the head of both swabs will be broken off and stored dry in a 5ml tube at -80°C for later testing with Ultra and the LumiraDx platform.

This project is part of the EDCTP2 programme supported by the European Union

13. Statistical considerations and data analysis

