#### 4.4 Study Variables

The Baseline participants variables we will collected from TB-CAPT-HIV EXULTANT-BaselineCharacteristics-v3, and the following versions of this document. From this CRF the important variables for the analysis are:

Variable		Used in
Label	name	
Date of enrolment	ENROL_D	To calculate endpoints related to time.
Time of enrolment	ENROL_T	To calculate endpoints related to time.
Country	COUNTRY	To adjust some regression models.  For previous analysis about at random lost to follow up.
Sex	SEX	To describe the participant's profile.  For previous analysis about at random lost to follow up.
Ethnic group	ETHNIC ETHNIC_SPEC	To describe the participant's profile.  For previous analysis about at random lost to follow up.

Level of education	EDUCATION EDUCATION_SPEC	To describe the participant's profile.  For previous analysis about at random lost to follow up.
Employment Status	EMPLOYMENT EMPLOYMENT_SPEC	To describe the participant's profile.  For previous analysis about at random lost to follow up.
Type of Employment:  2.6 Is the patient employed as a health care worker?  2.7 Is the patient employed as a prison warder/work at a correctional facility?  2.8 Is the patient employed as a miner?	EMPL_HLTH_YN  EMPL_PRSN_YN  EMPL_MINE_YN	To describe the participant's profile.  For previous analysis about at random lost to follow up.
Early HIV positive result  3.1.1 Date of earliest HIV positive result:	HIV_POS_DATE	To describe the participant's profile.  For previous analysis about at random lost to follow up.
Current taking antiretroviral	ART_YN	To describe the participant's profile.  For previous analysis about at random lost to follow up.
Previous TB episodes	TB_TX_YN	To describe the participant's profile.  For previous analysis about at random lost to follow up.
Received BCG vaccination	BCG_YN	To describe the participant's profile.  For previous analysis about at random lost to follow up.

Participant live alone?		To describe the participant's profile.  For previous analysis about at random lost to follow up.
Patient taking cotrimoxazole?	CTX_YN	To describe the participant's profile.  For previous analysis about at random lost to follow up.
High blood pressure	HIGH_RR_YN	To describe the participant's profile.
Diabetes	DIABETES_YN	To describe the participant's profile.
Cardiac disease	CARDIAC_YN	To describe the participant's profile.
Epilepsy	EPILEPSY_YN	To describe the participant's profile.

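### HIV is ascertained more actively in the trial than in the retrospective local-care cohort, which can confound the non-randomised comparison with local care

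*Protocol*

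**What the plan says.** **Trial side.** Study staff look for new admissions each morning, and "only those with unknown or documented HIV-positive status will be approached to participate in the study" (protocol 10.1). The same section continues: "For those with unknown HIV status, a rapid antibody-based test will be performed", once consent is obtained. The inclusion criteria (protocol 9.2.2) require confirmed HIV and admit patients with or without previous antiretroviral therapy (ART), so a patient found positive by this test can be enrolled. Protocol 12.4 expects such patients: CD4 counts are planned for certain TB cases "as well as all newly identified HIV-positive cases". SAP 4.4 lists "Date of earliest HIV positive result" (HIV_POS_DATE), to be used for describing participants and for the check on loss to follow-up.

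**Local-care side.** Protocol 10.18 states: "We will retrospectively collect data of a cohort of consecutively hospitalized HIV-positive patients that were admitted prior to the trial initiation". On the source it says: "Data to allow the evaluation of primary objectives will be collected from medical records (source documents) in an anonymized fashion". Records are taken backwards in time until about 147 per site are reached, without consent. There is no study HIV test, and no rule on when or how HIV must have been documented.

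**The comparison.** Protocol 8.3 compares primary and secondary endpoints of the intervention arm with earlier local care. Protocol 9 and 10.18 extend this to either arm. Protocol 8.3 lists it as exploratory, while 9 and 10.18 call it a secondary objective. Protocol 10.18 says that it is not powered and will be analysed by site.

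**The concern.** A patient with HIV whom local care never tested can enter the trial but cannot enter the cohort. The two groups may therefore differ in the share of newly found HIV, and with it in ART status and probably CD4 count, before any TB test is done.

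The cohort exists because the control arm may differ from what sites actually do. A difference from the cohort will be read as an effect of the testing strategy. If TB frequency or mortality differs between newly found and previously known HIV, part of that difference would come from case mix. A larger sample does not remove such a bias. If the date of first HIV documentation is not collected in the cohort, no later analysis plan can separate the two.

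**Working it through.** **Inputs from the documents.** Confirmed TB 19% (control) and 26% (intervention), two-sided alpha 0.05, power 80%, 5% loss, 586 per arm (protocol 9.3, 13.1). Cohort of about 147 per site (protocol 10.18), or 4 × 147 = 588 in all.

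**The plan's own figure.** With pooled variance under the null and p̄ = 0.225:

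n = [1.96·√(2 × 0.225 × 0.775) + 0.8416·√(0.19 × 0.81 + 0.26 × 0.74)]² / 0.07² = 558 evaluable per arm.

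Allowing for 5% loss gives 558 × 1.05 = 586, or 558 / 0.95 = 588. The stated 586 is reproduced. It sizes the randomised comparison, and the documents give no size calculation for the comparison with local care.

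**Spurious difference.** Let p be the confirmed-TB proportion in previously known HIV, RR the ratio of that proportion in newly found to known HIV, and s_T and s_C the shares of newly found HIV in the trial arm and the cohort. With identical TB testing on both sides:

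difference = p × (RR − 1) × (s_T − s_C)

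The documents give none of s_T, s_C or RR. Assume p = 19%, and s_C = 0 as the extreme case. In percentage points:

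| s_T | RR = 1 | RR = 1.25 | RR = 1.5 | RR = 2 |
|---|---|---|---|---|
| 5% | 0 | 0.24 | 0.47 | 0.95 |
| 10% | 0 | 0.47 | 0.95 | 1.9 |
| 20% | 0 | 0.95 | 1.9 | 3.8 |
| 30% | 0 | 1.43 | 2.85 | 5.7 |

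If routine testing had found some of the cohort too, the figures shrink. With s_T = 20%, s_C = 10% and RR = 2, the difference is 19 × 1 × 0.10 = 1.9 points instead of 3.8. An RR below 1 reverses the sign.

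**Against the precision of the comparison.** At one site, with 147 against 147, power for 19% versus 26% is Φ[(0.07·√147 − 1.157) / 0.588] = 30%, and the difference detectable with 80% power is about 14 points. With all sites pooled (about 586 per group) it is about 7 points.

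The chance of a nominally significant result in the trial's favour, with no true effect, is 2.5% without bias. With bias it becomes:

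| Bias (points) | One site, 147 per group | Pooled, 586 per group |
|---|---|---|
| 1.9 | 6.0% | 12.6% |
| 3.8 | 12.3% | 35.9% |

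The bias is small against the noise at one site. It would matter more if the sites were pooled, which protocol 10.18 does not plan.

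**The case against.** **Newly diagnosed patients may be in the cohort.** A reader might infer that the cohort holds only patients known to be HIV-positive before admission. Protocol 10.18 does not say so. A patient first diagnosed by routine testing in the earlier admission is HIV-positive in the record and is not excluded, and protocol 9.1.1.2 notes HIV testing at the two Maputo hospitals. Likewise, a trial patient of unknown status at the morning visit might have been tested by routine care later in the stay. This stands: the difference is one of degree.

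**Direction is not documented.** A reader might infer that the trial arms will show more confirmed TB and worse mortality than local care for this reason. Neither document gives TB frequency or mortality by new versus known HIV. This also stands: confounding is possible, not shown.

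**The analysis may be specified elsewhere.** SAP 3.2 leaves the exploratory objectives to a separate SAP, and the contents of the Retrospective CRF (protocol 14.2) are not shown. This stands in part. It cannot be said that the CRF lacks the date. However, protocol 9 and 10.18 call the comparison secondary, and the exploratory sub-studies that protocol 13.2.3 names for separate plans do not include it.

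**Restriction changes the question.** Limiting both sides to previously known HIV drops patients diagnosed during admission, whose care is part of real local practice. This is a good reason to keep the full-cohort comparison as well.

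**Other differences remain.** The comparison is historical, protocol 10.7 concedes that data quality and completeness may differ by site, and 10.18 does not apply the trial's exclusion criteria to the cohort. This is true, but it does not justify leaving a difference that is easy to address.

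**Conclusion.** The concern holds in a limited form. The trial finds HIV actively and the records-based cohort cannot, and the plan makes no allowance for it. Following the plan therefore compares populations ascertained to different degrees, and the comparison with local care can be confounded.

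The size is 0 to about 4 points in confirmed TB, assuming 5–20% newly found in the trial, none in the cohort, a ratio of 1 to 2, and a 19% base. Newly diagnosed patients in the cohort would reduce it, and a ratio below 1 would reverse it. The documents offer no basis for a corresponding mortality figure.

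A reader might go further and infer that the primary result is biased. It is not: the HIV test establishes eligibility before randomisation (protocol 10.1 and 10.3 to 10.5) and applies to both arms alike, so every randomised comparison is untouched. What is affected is a non-randomised comparison that the protocol itself describes as unpowered.

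**What to change.** In protocol 8.3 and 10.18, and in the analysis plan that will cover this comparison:

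1. State how HIV status is ascertained in the cohort, and make sure the Retrospective CRF captures the date HIV was first documented.
2. Present the comparison with local care in patients whose HIV was documented before that admission, on both sides. In the trial this means HIV_POS_DATE earlier than the admission date. Protocol 10.8 has the admission date recorded, but SAP 4.4 does not list it among the analysis variables, so it should be added. Protocol 10.1 also accepts CD4 records or an ART prescription as proof of HIV, so say how patients with such proof but no test date are classified.
3. Show the full-cohort comparison alongside, and report newly found HIV separately on each side.

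The cost is at most one item on the Retrospective CRF, one variable and one filter. The restricted comparison will have fewer patients in an analysis that is already unpowered, and other historical and eligibility differences will remain. No randomised analysis and no clinical procedure changes.
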